**Table 2-2 Plasma PK samples schedule for week 1 and week 17**

Week 1

Day	Time point	PK sample #
1	0 h pre-dose	101
1	4 h postdose	102
1	7 h postdose	103
1	12 h post-dose	104
2	22 h post-dose	105
4	72 h post-dose	106
8	0 h pre-dose as well as 168 h post dose	107

Week 17

Day	Time point	PK sample #
113	0 h pre-dose	115
113	4 h postdose	116
113	7 h postdose	117
113	12 h post-dose	118
114	22 h post-dose	119

116	72 h post-dose	120
NA	168 h post dose will be imputed using 0 h pre-dose on day 113	NA

## Figures

Spaghetti plots for Ctrough will be presented over time (from week 2 to week 17).

All above analysis will be repeated for UFB112 plasma. In addition, ratio of UFB112/branaplam will be calculated for the PK parameters (Cmax and AUClast at week 1 and 17) and summarized in tables. The UFB112/branaplam ratio will be calculated as follows:

metabolite ratio =

(PK\_parameter\_UFB112/PK\_parameter\_LMI070) \* (molecular weight\_LMI070/molecular weight\_UFB112)

The molecular weights are 393.4 g/mol and 409.4 g/mol for branaplam and UFB112, respectively.

## PK parameters in CSF

### Summary tables

Branaplam concentrations (Ctrough) in CSF (ng/ml) and plasma (ng/ml) will be summarized at Week 9 and Week 17, as well as the mean concentration ratios: CSF/plasma and CSF/free plasma. The free plasma concentration will be calculated by multiplying the plasma concentration by the fraction unbound (fu: branaplam 0.349, fu UFB112: 0.0220, DMPK R1900562).

## Figures

Scatter plots of Ctrough in CSF vs. plasma will be presented to explore the correlation (color coded by visit 9 and 17).

All above analysis will be repeated for UFB112.

## Listings

Listings will be provided for all concentrations and PK plasma in both serum and CSF.

### 2.6.3 Handling of intercurrent events

Not applicable.

### 2.6.4 Handling of missing values not related to intercurrent event

The missing values will be treated as missing. Unless otherwise stated, missing data will not be inputted for the analysis.

## 2.7 Safety analyses

All safety analyses will be carried out based on the SAF. For some ECG, vital signs and lab assessments, if time is expected but missing at the end of study visit, will be imputed as 0 hour pre-dose as applicable.

### 2.7.1 Adverse events (AEs)

AEs will be considered as treatment-emergent (TEAE) if the event is starting after the start of double-blind treatment or the event is present prior to start of double-blind treatment but increased in severity after the start of treatment based on preferred term. This assumes the same AE with increased severity is properly entered as a separate record in the database with start date being the date when severity increases and that a second AE with same severity won't be entered before the same AE is resolved.

Adverse events will be coded using the MedDRA dictionary and presented by system organ class (SOC) and preferred term (PT). The MedDRA version used for reporting the study will be described in a footnote on AE related outputs.

Additionally, Participant with AEs indicative of neurotoxicity / peripheral neuropathy (listed in [Table 2-3](#)) will be flagged at participants level for recovery.

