- Upon receipt of the communication, the sites were to contact participants as soon as possible informing them of the following and documenting the conversation in the source medical records:
 - Development of branaplam in HD has been terminated due to the high incidence of signals of neurotoxicity at the current dose of branaplam and the low likelihood that lower doses or different dose regimens can be identified that would be safe and provide clinically meaningful benefit. All topics in the Talking Points in the USM must be included in the discussion with the participants; these points explain the safety findings observed in VIBRANT-HD, the rationale for not resuming treatment, and the importance for participants in the active arm to continue study visits.
 - Dosing in the VIBRANT-HD study is permanently discontinued, and no further cohorts will be started.
 - The treatment arm to which they were randomized. Allocation to treatment may be shared with participants either during an upcoming visit or over the phone.
 - Participants randomized to placebo do not require additional safety assessments and can be discontinued from the study at their upcoming Week 33 visit or immediately if this visit has already been completed. The EOT and End of Study (EOS) dispositions can be declared.
 - Participants randomized to branaplam are requested to continue assessments for approximately one year from last dose (as defined below).
 - Novartis has prepared a separate letter for the trial participants that will be sent to them, in local language, if required as per local law and regulation.

With respect to the follow up schedule of assessments per USM, refer to [Table 8-5](#).

Upon completion of the final Week 69 visit, the EOT and the End of Study dispositions (EOS) can be declared for each participant.

Participants that had already permanently discontinued study treatment and had scheduled an EOT and/or follow up assessments at the time of the USM dated 05-Aug-2022 should continue the previously agreed upon schedule of assessments as per discussions between Investigator and Sponsor.

These actions were to be implemented immediately, prior to Institutional Review Board (IRB)/Independent Ethics Committee (IEC) or Health Authority (HA) approval. Last Patient Last Treatment (LPLT) in the VIBRANT-HD trial occurred 08-Aug-2022.

Changes to the protocol:

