6.4 Treatment blinding

Per the USM, the sites, Investigators and participants were unblinded on 07-Dec-2022. The Sponsor study team was unblinded on 02-Nov-2022.

Pre-USM: For the Core Period, participants, Investigator staff, persons performing the assessments, and Sponsor study team will remain blind to the identity of the treatment within each cohort from the time of randomization until interim analysis for the Core Period using the following methods: Randomization data are kept strictly confidential until the time of unblinding and will not be accessible by anyone else involved in the study with the following exceptions: independent PK analyst, independent statistician and independent programmer supporting the Cohort Gating Decision Board and the DMC members.

- The identity of the treatments will be concealed by the use of study treatment that are all identical in packaging, labeling, schedule of administration, appearance, taste, and odor.
- The randomization codes associated with participants from whom PK samples are taken will be disclosed to PK analysts who will keep PK results confidential until data base lock.
- The data with a potential to unblind recipients (typically markers of the treatment effect) will be stored in a restricted area of the database until database lock. Although the randomization list and/or treatment allocation information will NOT be communicated to them, the following personnel will be considered as unblinded due to the results post-baseline:
 - HD biomarker analysts (data including but not limited to HTT/mHTT in plasma (protein [REDACTED]), [REDACTED] and CSF (protein [REDACTED]))
 - All other data with potential for unblinding i.e., tolerability data) will be treated similarly as randomization data with regards to blinding: the data will be loaded into a restricted area. Access will only be granted to members of the authorized independent unblinded team.

Unblinding during the Core period will occur in the case of participant emergencies.

In the open-label extension (OLE), treatment will be open to participants, Investigator staff, persons performing the assessments, and the Clinical Trial Team (CTT).

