Days	1	29	57	85	113	141	169	197	225	253	281	309	337	365	999
Weeks	1	5	9	13	17	21	25	29	33	37	41	45	49	53	143

that they are performed only once as part of the OLE baseline visit, such as LP and MRI.

² Participants who discontinue study treatment should be scheduled for an EOT Open-label visit at which time all of the assessments listed for the EOT open-label visit will be performed. A 30-day safety follow up period after the last open label study treatment dose was taken must be observed.

³ Findings must be recorded on the appropriate Adverse Events eCRF

⁴ Male patients only

⁵ Serum pregnancy test is collected as part of the blood chemistry. Refer to [Section 8.4.3](#) for positive result follow up action

⁶ Urine dipstick done at site; if findings then send urine to central lab for microanalysis

⁷ Echocardiogram with GLS

⁸ For visits where samples are collected only once a day, they must always be collected at approximately the same time of the day

⁹ Serum Biomarkers, including NFL. See Biomarkers Assessments in Blood and CSF, [Section 8.5.3](#)

¹⁰ Pre-dose

¹¹ Randomization will be done if there is more than one dose chosen

¹² IRT call and drug preparation by site personnel

¹³ Weekly dosing, not reflected on the VES, should be confirmed with weekly telephone calls to the participant and will be collected on the eCRF.

¹⁴ Update as necessary

¹⁵ To minimize burden to patients, it is recommended that Post-baseline MRI and UHDRS assessments are done up to 1 day prior to the planned study drug dosing date at any given visit. If done same day as Lumbar Puncture, MRI and UHDRS should be done first

The table below (see [Table 8-5](#)) reflects the changes in the USM follow-up notification dated 06-Dec-2022.

Participants randomized to placebo do not require additional safety assessments and can be discontinued from the study at the Week 33 visit or immediately if this visit was already completed. The End of Treatment and End of Study (EOS) dispositions can be declared. Participants that had already permanently discontinued study treatment and had scheduled an EOT and/or follow up assessments at the time of the USM follow-up notification dated 06-Dec-2022 should have follow up (FU) assessments as closely as possible to Assessment [Table 8-5](#).

Table 8-5 Assessment Schedule Urgent Safety Measure

Period	Revised follow-up assessment schedule ³			
Visit Name	Wk 33	Wk 53	Week 69	EOS
Days	225	365	477	477
Weeks	33	53	69	69
Physical Examination	S	S	S	

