Neurological Examination	X	X	X	
Vital signs (including body weight)	X	X	X	
Electrocardiogram (ECG)	X			
Hematology	X	X ¹	X ¹	
Clinical Chemistry	X	X ¹	X ¹	
Thyroid Function	X	X ¹	X ¹	
NTproBNP, Troponin	X	X ¹	X ¹	
Pregnancy Test - Serum	X	X	X	
Urinalysis	X	X ¹	X ¹	
Columbia- Suicide Severity Rating Scale (C-SSRS)	X	X	X	
Serum Biomarkers (NfL)	X	X	X	
Nerve Conduction Studies (tibial CMAP/sural nerve SNAP) ²	X	X	X	
Brain MRI	X	X	X	
UHDRS – TFC, TMS, IS, █	X		X	
Adverse Events	X	X	X	
Serious Adverse Events	X	X	X	
Prior and concomitant medications or therapies	X	X	X	
End of Study Disposition				X

Period	Revised follow-up assessment schedule ³			
Visit Name	Wk 33	Wk 53	Week 69	EOS
Days	225	365	477	477
Weeks	33	53	69	69

¹ To minimize burden to participants, it is recommended that safety labs/urinalysis are performed only if required for Adverse Events or follow up of an AE.

² NCS must be performed in triplicate and recommended bilaterally. However, if performed unilaterally, then it should be conducted on the same side as per the screening visit

³ Visit window for Week 33 onwards is ± 2 weeks.

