12.5.2 Safety endpoints

As per the USM, the OLE period is no longer applicable. Safety analyses will be carried out based on the SAF cumulatively.

As one of the primary endpoint, safety analyses will be carried out based on the SAF for summaries including Core Period data, OLSAF for summaries using only OLE data:

- IA: all safety data from baseline to a cut-off date (a date pre-specified for iDBL) will be reviewed by treatment group.
- End of study: all safety data will be reported cumulatively (Core + OLE) and by two periods separately:
 1. Core period (DRF + BE: this would partially overlap with IA, plus the data from BE that were not reported at IA) by treatment group
 2. OLE period by treatment group (only if more than one dose is selected for OLE) and by treatment group originally assigned in the core period

Adverse events

The number (and percentage) of participants with treatment emergent AEs will be summarized in the following ways:

- By primary system organ class and preferred term.
- By primary system organ class, preferred term and maximum severity.
- By Standardized MedDRA Query (SMQ) and preferred term.

Separate summaries will be provided for SAEs, deaths, and study medication related AEs, AEs leading to study discontinuation and AEs leading to study drug interruption/discontinuation.

Vital signs

Number and percentage of participants with clinically notable vital signs will be presented. Participants with clinically notable vital signs will be defined in the SAP.

Cardiac assessments

Cardiac assessments will include 12-lead ECG, Echocardiogram (ECHO) with GLS, and cardiac enzymes (Troponin and NTproBNP). For each assessment, summary statistics will be

provided for each individual parameter, as appropriate. Number and percentage of participants with clinically significant abnormalities will be calculated.

Clinical laboratory evaluations

The number and percentage of patients with newly occurring or worsening laboratory abnormalities meeting the clinically notable criteria (to be defined in the SAP) will be summarized by laboratory parameter. The most extreme post-dose value is considered. For selected laboratory tests (e.g., liver enzyme abnormalities), summary statistics of change from BL laboratory results will be presented by laboratory test category, visit and treatment group.

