#### 2.1.1 General definitions

##### Treatment groups

Due to USM, only Cohort 1 was initiated. All analysis will be performed by treatment group within cohort 1:

- Cohort 1: LMI070 56 mg and Placebo

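### Treatment-emergent events and any-post-baseline safety counts have no common end date, while placebo may leave at Week 33 and branaplam is followed to Week 69

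*SAP*

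**What the plan says.** - SAP 2.7.1: "AEs will be considered as treatment-emergent (TEAE) if the event is starting after the start of double-blind treatment", or if a pre-existing event worsens after that point. No end date is given, for example a fixed number of days after last dose.
- Protocol 12.5.2, post-USM text: "Safety analyses will be carried out based on the SAF cumulatively". SAP 2.1.1: "All analysis will be performed by treatment group within cohort 1".
- The tables are counts and percentages by arm. Those for vital signs (2.7.4.2), C-SSRS (2.7.4.3), nerve conduction (2.7.4.6) and any increase in serum NfL (2.11.1) count a qualifying value at any post-baseline time or visit. Those for the neurological examination (2.7.4.4) and neuropathy questionnaire (2.7.4.5) use two-consecutive-visit flags, and the questionnaire also has an any-visit version. In SAP Table 5-2 the Week 69 window is open-ended.
- Protocol Section 8, above Table 8-5: "Participants randomized to placebo do not require additional safety assessments and can be discontinued from the study at the Week 33 visit", or immediately if that visit has already taken place. The Amendment 02 actions ask branaplam participants to continue for about a year after their last dose. Table 8-5 ends at Week 69, and AEs, SAEs, vital signs with weight, C-SSRS, neurological examination, nerve conduction and serum NfL remain scheduled at Weeks 53 and 69.
- Protocol 6.4: "Per the USM, the sites, Investigators and participants were unblinded on 07-Dec-2022". Protocol 6.1 dates the last dose 08-Aug-2022.

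**The concern.** Follow-up differs by arm by design, not through random dropout. A percentage of participants with at least one event can only rise with follow-up, so the longer-followed arm is read against a shorter-followed one. Findings made late, off drug and with allocation known can enter almost only the branaplam column, yet under the definition an event many months after the last dose still counts as treatment-emergent.

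Safety is one of the two primary objectives (protocol 12.4), and summary results for primary endpoints will be disclosed (protocol 13.2). Readers will set the two columns side by side as like for like.

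The tables affected are:
- TEAEs and adverse events of special interest;
- vital signs, including weight, and C-SSRS;
- neurological examination, neuropathy questionnaire (its post-USM schedule is not visible in Table 8-5) and nerve conduction;
- any increase in serum NfL.

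ECG, echocardiogram, CSF NfL and TEAEs leading to dose interruption or discontinuation are little affected. By-visit tables and the active-only neurological summary (SAP 2.7.4.7) are not affected.

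**Working it through.** The plan states no figure for this point, so there is none to reproduce. The sizes below are illustrations; event rates, actual arm sizes and actual follow-up are not in the documents.

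**Inputs from the documents.** Week 33 is Day 225 and Week 69 is Day 477 (protocol Table 8-5). "Visit window for Week 33 onwards is ± 2 weeks" (Table 8-5, footnote 3). Planned Cohort 1 size is about 25 at 4:1, so about 20 branaplam and 5 placebo. The SAP Week 33 window ends on Day 239 (Table 5-2).

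**Follow-up ratio.** 477/225 = 2.12. Using the ±2-week windows it runs from 463/239 = 1.94 to 491/211 = 2.33.

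**No drug effect, unequal follow-up.** Let p be the incidence in both arms by the day E on which placebo leaves, and f the later hazard relative to the earlier one. Branaplam incidence by Day 477 is 1 − (1 − p)^k, with k = 1 + f(477 − E)/E. For E = 225, k = 1 + 1.12f. For E = 337 (the Week 49 visit day, for placebo participants already past Week 33), k = 1 + 0.415f.

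| Placebo leaves | Placebo reads | f = 0 | f = 0.25 | f = 0.5 | f = 1 |
|---|---|---|---|---|---|
| Day 225 | 10% | 10% | 12.6% | 15.2% | 20.0% |
| Day 225 | 20% | 20% | 24.8% | 29.4% | 37.7% |
| Day 337 | 10% | 10% | 11.0% | 11.9% | 13.9% |

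In participants, the first row is 20 × 0.100 = 2.0, then 2.5, 3.0 and 4.0 of 20. If only half the branaplam participants stay to Week 69, the constant-hazard figure is 0.5 × 10% + 0.5 × 20.0% = 15.0%.

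**Placebo precision.** One participant of 5 is 20 percentage points. For 0/5 the exact 95% upper limit is 1 − 0.025^(1/5) = 52%.

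**Number of looks.** These figures assume a per-look chance of a false flag.
- Nerve conduction: three scheduled post-baseline looks on branaplam (Weeks 33, 53, 69) against at most one on placebo. A 10% chance reads between 10% (fully correlated looks) and 1 − 0.9³ = 27% (independent looks, an upper illustration). A 5% chance reads between 5% and 1 − 0.95³ = 14%.
- Serum NfL: ten scheduled looks to Week 33 (Weeks 2, 3, 5, 9, 13, 17, 21, 25, 29, 33) against twelve with Weeks 53 and 69. A 10% cumulative chance over ten looks becomes 1 − 0.9^(12/10) = 11.9%, assuming independence.
- No look-based figure is given for the two-consecutive-visit flags.

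**Effect of a common cut.** With the same study day in both arms, the no-effect case gives equal percentages. Placebo may leave from Day 225 − 14 = Day 211, so a Day 239 cut leaves up to 28 days of mismatch: 10% against 1 − 0.9^(239/211) = 11.2% at constant hazard.

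**The case against.** The strongest reply is that this is a descriptive, abbreviated report on a terminated programme. With about 5 placebo participants, a shift of 0 to 2 branaplam participants lies below what the comparison can resolve. The neurotoxicity findings arose after 9 to 13 weeks on treatment. The SAP already plans individual follow-up plots with on/off-treatment shading, a follow-up summary and full AE listings, so a footnote might be enough. All of this is true. It limits the consequence, but small numbers add imprecision and do not remove a distortion that runs in one direction. The displays show the imbalance without bounding any percentage.

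The SAP also defines a visit-level on/off-treatment flag (2.1.1) for several endpoints, including nerve conduction, neurological examination and neuropathy symptoms. The flag is not applied to the frequency tables at issue, and its visible list does not name AEs, vital signs or C-SSRS. An on-treatment table would be a reasonable alternative, though with a shorter window.

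After 30 days off drug, SAEs go to the sponsor's safety database only if causality is suspected (protocol 10.1.3). Table 8-5 nevertheless collects SAEs at Weeks 53 and 69, so serious events are not exempt.

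A study-day cut equalises duration only. Some findings before the cut will still be off drug or unblinded, in both arms. That stands, and the report should say so.

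**Conclusion.** The concern holds. The TEAE window and the any-post-baseline counts are open-ended, follow-up is unequal by design, and nothing in the SAP restricts the affected by-arm percentages to a common period. The direction is upward on branaplam, provided first events can occur after placebo has left. The size is unknown. In the no-effect illustration with 10% incidence by Day 225 it ranges from zero to 10 percentage points, and it is smaller if placebo stays longer or branaplam participants leave early. Because nothing is tested, the consequence is a misleading descriptive contrast, not a type I error. The change should be made. It does not alter the conclusion on neurotoxicity.

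**What to change.** 1. For each affected table, add a by-arm version counting only findings with onset up to one common study day in both arms, and use it for the between-arm reading. For two-consecutive-visit flags, both visits must fall on or before the cut.
2. State the day chosen. Day 239 keeps the whole SAP Week 33 window but leaves up to 28 days of mismatch; Day 211 removes the mismatch but loses some Week 33 findings.
3. State how an AE with no usable onset date is handled. SAP 5.1.2 treats it as post-dosing, but Table 5-1 leaves its date empty.
4. Keep the cumulative tables that protocol 12.5.2 requires, with a footnote that follow-up is unequal between arms, partly off drug and partly unblinded.
5. Show later branaplam findings in a separate active-only table. Recovery stays in the active-only table of SAP 2.7.4.7.
6. For nerve conduction, show the number tested per arm and visit. Note that tests before Week 33 were finding-driven or case by case, so those tested are not a clean denominator.
7. Label laboratory samples after Week 33 as AE-driven, since the protocol recommends that "safety labs/urinalysis are performed only if required for Adverse Events or follow up of an AE".

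The cost is SAP wording, one date flag, re-derived consecutive-visit flags, one extra set of tables, and footnotes. No new data are needed and no cumulative table is removed. The downside is more output for a small descriptive comparison.

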**Table 2-3 AEs indicative of neuro toxicity / peripheral neuropathy**

SOC	Preferred Term	Reported term
Nervous system disorders	Axonal and demyelinating polyneuropathy	SENSOMOTORIC AXONAL POLYNEUROPATHY
Nervous system disorders	Axonal neuropathy	AXONAL NERVE CONDUCTION CHANGE
Nervous system disorders	Coordination abnormal	HAND COORDINATION PROBLEM
Nervous system disorders	Electric shock sensation	PAIN LIKE ELECTRIC SHOCK RIGHT THIGH
Nervous system disorders	Hypogeusia	HYPOGEUSIA
Nervous system disorders	Hyporeflexia	DECREASE IN REFLEXES
Nervous system disorders	Loss of proprioception	PROPRIOCEPTIVE DIFFICULTY IN THE HANDS BILATERALLY
Nervous system disorders	Neuralgia	NEUROPATHIC PAIN
Nervous system disorders	Neuropathy peripheral	NEUROPATHIE
Nervous system disorders	Paraesthesia	TINGLING IN THE UPPER EXTREMITIES
Nervous system disorders	Paraesthesia	TINGLING IN THE LOWER EXTREMITIES
Nervous system disorders	Paraesthesia	PARESTHESIA
Nervous system disorders	Paraesthesia	PARESTHESIA (BILATERAL)

SOC	Preferred Term	Reported term
Nervous system disorders	Paraesthesia	TINGLING IN THE HANDS AND FEET
Nervous system disorders	Peripheral sensory neuropathy	SENSORY NEUROPATHY
Nervous system disorders	Polyneuropathy	POLYNEUROPATHY
Gastrointestinal disorders	Oral discomfort	BURNING MOUTH
		*THICK FIBER SENSORY POLYNEUROPATHY PREDOMINANTLY LOWER EXTREMITIES ENGLISH

\* Reported term/SOC has not been coded and is subject to change

